7.1 Potential adverse events related to intervention

The risk of any significant adverse event occurring is deemed unlikely. All reasonable measures to avoid these events will be undertaken. Any adverse events (as described below) that occur will be recorded and reported in any trial data:

1. Bleeding requiring takeback to theatre for haemostasis or requiring transfusion of >1 unit packed red cells with corresponding drop in Hb >1g/dl ;
2. Venous thrombo-embolism;
3. Myocardial infarction;
4. Adverse reaction to local anaesthetic;
5. Major ipsilateral amputation, either below-knee amputation or above-knee amputation

7.2 Definition of an adverse event

Any untoward medical event related directly or indirectly to an intervention as a result of participation in the trial.

7.3 Definition of a serious adverse event

Any unexpected event that results in death; a life-threatening adverse event; in-patient hospitalisation or prolongation of existing hospitalization; a persistent or significant incapacity or substantial disruption of the ability to conduct normal life functions; or a congenital anomaly/birth defect is deemed a serious adverse event.

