7.4 Event Reporting

All adverse events will be reported directly to the either the site or principal investigator. Recurrent adverse events or serious adverse events in isolation will be reported in turn to the local Ethical Committee and the risk assessment department for risk analysis.

8. Statistical considerations:

Post intervention, all patient outcomes will be recorded and assessed on intention to treat basis. We expect a certain degree of crossover from the bone cutter trial arm to bone saw trial arm, as is reflected in daily surgical practice. Furthermore, we expect a small number of patients may ultimately not undergo treatment as initially planned. Any losses to follow up will be reported. There are no studies investigating this particular trial question, as such there is no data on which to base a power calculation. For this pilot trial, we aim to recruit 20 patients into each arm i.e. 40 patients in total. All analyses will be performed on an intention to treat basis. The statistical analysis will be blinded. Binary outcomes will be analysed using the Chi-Square test. Non-parametric continuous variables will be compared using Mann-Whitney U Test. The time between surgery and measurable endpoints will be compared using Kaplan-Meier Survival Curves.

9. Ethical Considerations:

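### Section 7.3 builds 'unexpected' into the definition of a serious adverse event, so under 7.4 some serious events regarded as expected need not reach the ethics committee

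*Combined protocol and SAP*

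**What the plan says.** Four short sections govern safety reporting.

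- **7.1** names five kinds of event in advance, among them myocardial infarction and "Major ipsilateral amputation, either below-knee amputation or above-knee amputation", and says that they will be captured in the trial data. It also states: "The risk of any significant adverse event occurring is deemed unlikely".
- **7.2** defines an AE as "Any untoward medical event related directly or indirectly to an intervention as a result of participation in the trial".
- **7.3** defines an SAE. It begins "Any unexpected event that results in death; a life-threatening adverse event; in-patient hospitalisation or prolongation of existing hospitalization" and continues with "a persistent or significant incapacity or substantial disruption of the ability to conduct normal life functions" and congenital anomaly.
- **7.4** has two levels. First, "All adverse events will be reported directly to the either the site or principal investigator". Then: "Recurrent adverse events or serious adverse events in isolation will be reported in turn to the local Ethical Committee", together with the risk assessment department.

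No section lists which events count as expected, defines 'recurrent', or says who judges expectedness or relatedness. Section 9.1 deals with ethical approval only and adds no reporting route.

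**The concern.** How serious an event is, whether it was expected and whether it is related to the intervention are three separate questions. Seriousness should depend on the outcome alone. Expectedness and relatedness can then decide how fast, and to whom, an event is reported. Section 7.3 makes expectedness a condition of being serious at all, and 7.4 uses the resulting label as the only route by which a single event reaches the ethics committee. A serious event that someone regards as expected can therefore drop out of the committee's view by definition, with no one having decided that it should.

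Expectedness is also hard to settle from this protocol. The background section describes re-amputation and readmission as well documented and cites major amputation in 14.4% of a published Irish cohort, while 7.1 calls significant events unlikely. Two investigators could apply the same text to the same major amputation and classify it differently.

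**Working it through.** The plan gives no figure to reproduce on this point, so the check is mainly a reading of the text.

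**Step 1. Two readings of 7.3.** The punctuation allows 'unexpected' to govern either the whole list or only the event that results in death.

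| Event | 'Unexpected' governs the whole list | 'Unexpected' governs death only |
|---|---|---|
| Infarction with admission, regarded as expected | Not an SAE | SAE (hospitalisation) |
| Major amputation, regarded as expected | Not an SAE | SAE (hospitalisation or incapacity) |
| Expected death with hospitalisation | Not an SAE | SAE (hospitalisation) |
| Expected death, no hospitalisation, judged related | Not an SAE | SAE only if classed as a life-threatening AE |
| Expected death, no hospitalisation, judged unrelated | Not an SAE | Not an SAE: the life-threatening item uses the term defined in 7.2, which requires relatedness |

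A gap remains on both readings. It is wide on the first and narrow on the second.

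**Step 2. What 7.4 then requires.** An event that is not an SAE reaches the committee only as a recurrent AE. If 'recurrent' means a second event of the kind in the trial, the first one waits. If it means a second event in the same patient, each patient's first event stays outside.

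**Step 3. The separate effect of 7.2.** An event judged unrelated is not an AE. It therefore falls outside the duty to report AEs to the investigator and outside the recurrence route. This does not depend on 'unexpected' and is not needed for steps 1 and 2. The definitions also fail to nest: 7.3 opens with 'event', so an unexpected death judged unrelated is an SAE as written although it is not an AE under 7.2.

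**Step 4. Scale, first reading only.** Inputs: n = 40 (section 8) and p = 21/146 = 0.144 for major amputation (background section; the protocol does not give that cohort's follow-up). Assumptions: every major amputation is regarded as expected, each is an AE under 7.2, and 'recurrent' means a second event in the trial.

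- Expected number: 40 × 21/146 = 5.75.
- Exactly one event, so never escalated: 40 × p × (1 − p)^39 = 0.0135, about 1%.
- Two or more events: 0.9845, about 98%.

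At this rate recurrence would almost always occur, and the effect is to delay the first report. At an assumed rate of 5%, the chance of exactly one event would be 40 × 0.05 × 0.95^39 = 0.27. The answer moves from 1% to 27% with the assumed rate, so it is not used as a measure of the defect.

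**The case against.** The strongest case on the other side is that little is lost. The events listed in 7.1 are recorded, 6.1 has post-operative complications recorded, section 8 says "all patient outcomes will be recorded and assessed on intention to treat basis", and AEs go to the site or principal investigator under 7.4. All of this stands. A reader might infer that serious events go unrecorded or that the safety comparison between arms is biased; the documents do not support either. Recording does not, however, supply a route to the committee.

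A second objection is that being listed in 7.1 does not make an event expected. That is right. Because 7.1 calls significant events unlikely, a site could treat a first infarction or major amputation as unexpected and report it. It would therefore be too strong to say that the plan excludes these events from committee reporting. What stands is that the text permits either classification.

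Third, the gap on the narrow reading is small, and the words 'directly or indirectly' in 7.2 limit how many events would be judged unrelated. Both are true. A reader might also treat relatedness and expectedness as one joint cause of the committee gap, but the relatedness limit is a separate matter.

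Finally, variation between sites is partly prospective. Section 4.4 calls the trial multicentre, but 3.1 has other centres still under evaluation and section 10 plans more sites after the initial cohort. Different investigators within one centre could still differ.

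**Conclusion.** The point holds as a defect of wording in safety oversight, of minor to should-fix severity. On either reading of 7.3, at least one kind of serious event, the expected death without hospitalisation that is not classed as a life-threatening AE, need not reach the ethics committee as a single event. On the wider reading the same is true of any first serious event regarded as expected. Separately, events judged unrelated leave the AE reporting chain through 7.2.

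No share or number of missed events is claimed. The documents give no mortality rate and no rule for expectedness, and the one rate that they do cite points mainly to delay. The finding is firm on the text and makes no claim about how investigators would behave: a site that treated every death as unexpected would report them all. The primary safety endpoint and every comparison between arms stand as planned.

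**What to change.** - **7.3:** delete 'unexpected', so that seriousness depends on outcome alone and any death is an SAE.
- **7.2:** define an AE as any untoward medical occurrence in a randomised participant, whether or not related. Record relatedness and expectedness as two separate fields.
- **7.4:** define or remove 'recurrent', and state that every SAE goes to the ethics committee, saying which go promptly and which in a periodic summary.

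A periodic summary would not by itself remove the delay for a first event. It would make the timing a stated rule instead of a by-product of how a site labels the event, so the split between the two routes must be written down.

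The cost is a few changes of wording, two fields on the event form and some additional forms. Many of the added SAEs would be events that the trial already collects as outcomes. At the cited 63/146 for further ipsilateral amputation, 40 × 63/146 is about 17 patients, if each were admitted and that cohort's unstated follow-up were comparable. No analysis or sample size changes.

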7.4 Event Reporting

All adverse events will be reported directly to the either the site or principal investigator. Recurrent adverse events or serious adverse events in isolation will be reported in turn to the local Ethical Committee and the risk assessment department for risk analysis.

8. Statistical considerations:

Post intervention, all patient outcomes will be recorded and assessed on intention to treat basis. We expect a certain degree of crossover from the bone cutter trial arm to bone saw trial arm, as is reflected in daily surgical practice. Furthermore, we expect a small number of patients may ultimately not undergo treatment as initially planned. Any losses to follow up will be reported. There are no studies investigating this particular trial question, as such there is no data on which to base a power calculation. For this pilot trial, we aim to recruit 20 patients into each arm i.e. 40 patients in total. All analyses will be performed on an intention to treat basis. The statistical analysis will be blinded. Binary outcomes will be analysed using the Chi-Square test. Non-parametric continuous variables will be compared using Mann-Whitney U Test. The time between surgery and measurable endpoints will be compared using Kaplan-Meier Survival Curves.

9. Ethical Considerations:

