Re-ulceration, re-infection, re-amputation and hospital re-admission after partial foot amputation for digital gangrene is well documented in the literature in both diabetic and PAD cohorts(6). Across the literature, rates of re-amputation at five years post-index surgery for diabetic foot complications range from 45-65% (6, 7). A recent study by Collins et al reported that, out of 146 Irish patients undergoing minor amputations, 43% (n=63) required further ipsilateral amputation, 21 (14.4%) of which were trans-tibial or trans-femoral(8). Chronic kidney disease, diabetes with or without poor glycaemic control, peripheral neuropathy, peripheral arterial disease, ongoing tobacco smoking, obesity (BMI >30), concurrent sepsis at the time of index operation have all been identified as independent risk factors for amputation failure and the need for revision(9-11). While numerous studies have investigated patient-dependent factors predictive of amputation failure, there is a dearth of evidence examining the impact of surgical technique on this commonly performed procedure.

An exhaustive search of the literature surrounding surgical technique and outcomes after ray amputation yielded several papers on the benefits of various soft tissue flaps for covering wound defects but just one detailing a particular methods of bone transection. However, Moodley et al focused on the use of a Gigli saw, which is beyond the scope of this feasibility

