3.1 Statement of Design

This is a prospective, randomised controlled, assessor-blinded, feasibility study with participants allocated to one of two parallel groups in a 1:1 fashion using randomisation by minimisation. The operating surgeon will be aware of the type of operation performed. The nature of the intervention (metatarsal amputation using either a bone saw or a bone cutter) ensures that both the patient and the assessor can be blinded, so long as the assessor is not the operating surgeon. Patients who are undergoing toe amputation via spinal or local anaesthesia, will be provided with headphones to ensure they do not overhear what equipment is requested. Evaluation of the post-operative x-rays will be performed by a designated trial radiologist who will be blinded to the intervention. The statistical analysis will be blinded. The primary trial centre will be University Hospital Galway, Ireland, with other centres also evaluated for inclusion. Appropriate patients shall be recruited from both the out-patient and in-patient setting. The procedures may be classed as Emergent, Urgent or Elective.

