3.2 Endpoints

3.2.1 Primary Efficacy Endpoint

The primary efficacy endpoint will be the number of patients in each group who underwent surgical reintervention at twelve months post-operatively.

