4.1 Inclusion Criteria

Consenting patients, aged 18 and over, undergoing transmetatarsal amputation of one or more toes. Patients will be stratified by pulse status (at least one pedal palpable vs both pedal pulses impalpable) and chronic kidney disease (eGFR >60 and eGFR <60 mL/min/1.73m²), considering both are significant factors in predicting wound healing.

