4.4 Randomisation

As this is a multicentre trial and considering the myriad of factors impacting healing after toe amputation, randomisation by minimisation will be generated centrally by third-party computer software (Sealed Envelope) to ensure equal distribution of patients in each cohort across the sites. Patients will be randomised in a 1:1 ratio. On the day of surgery, a nominated, independent member of the surgical team will access the randomisation software and show the operating surgeon. Of note, randomisation will be per patient and not per toe amputation; as such, a single patient undergoing two or more toe amputations simultaneously will only be randomised once.

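### The planned Chi-Square and Mann-Whitney tests leave out pulse status and eGFR group, the factors used to balance the arms, so they run below their nominal level and lose some power if those factors are prognostic

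*Combined protocol and SAP*

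**What the plan says.** Section 4.1: "Patients will be stratified by pulse status (at least one pedal palpable vs both pedal pulses impalpable) and chronic kidney disease", the reason given being "considering both are significant factors in predicting wound healing". The kidney levels are written "eGFR >60 and eGFR <60".

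The background section names chronic kidney disease and peripheral arterial disease among factors that "have all been identified as independent risk factors for amputation failure and the need for revision".

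Section 3.1: participants are "allocated to one of two parallel groups in a 1:1 fashion using randomisation by minimisation". Section 4.4 gives the purpose of minimisation as "to ensure equal distribution of patients in each cohort across the sites" and does not list its factors.

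Section 3.2.1 sets the primary efficacy endpoint as "the number of patients in each group who underwent surgical reintervention at twelve months post-operatively".

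Section 8: "Binary outcomes will be analysed using the Chi-Square test". Non-normal continuous variables get Mann-Whitney, and times get Kaplan-Meier curves with no test named. The target is 20 per arm, 40 in all, with no alpha, effect size or power. No adjusted or stratified analysis appears anywhere in the document.

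**The concern.** Balancing the arms on prognostic factors makes the difference between arms less variable than it would be under unrestricted randomisation. An unadjusted test still uses the larger variance. Its rejection rate under the null therefore falls below the nominal level, and a real difference is somewhat less likely to be detected.

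This bears on the 12-month reintervention endpoint and the ten comparative objectives in Section 2.2. It does not bear on the primary objective of collecting data for a later power calculation, and no effect on the size of the future trial is claimed.

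Three related gaps sit alongside:
- the minimisation factors are not listed;
- an eGFR of exactly 60 belongs to neither level;
- time outcomes are to be compared by curves alone.

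**Working it through.** **No figure to reproduce.** The 40 patients are a target, not the result of a power calculation.

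**Inputs from the document:** N = 40, 1:1 minimisation, two binary factors, Chi-Square and Mann-Whitney tests.

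**Assumptions, none given in the document:** two-sided 5% level; each factor present in 50% of patients; minimisation probability 0.8; equal odds ratio (OR) for each factor; 43% overall event rate. The 43% is the further ipsilateral amputation figure in the background section, from a different cohort and for a different outcome.

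**Step 1. Approximate size by hand.** Chi-Square uses a variance proportional to p(1−p) = 0.43 × 0.57 = 0.2451. If the arms are balanced on the factors, the variance that applies is the average within-stratum value, mean of p_k(1−p_k) over the four strata. With R the ratio of the second to the first, the size is about 2 × [1 − Φ(1.96/√R)].

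| OR per factor | Stratum risks (neither, one, both) | Within-stratum variance | R | 1.96/√R | Approximate size |
|---|---|---|---|---|---|
| 1 | 43%, 43%, 43% | 0.2451 | 1.000 | 1.960 | 5.0% |
| 2 | 27%, 43%, 60% | 0.2317 | 0.946 | 2.016 | 4.4% |
| 3 | 19%, 42%, 69% | 0.2149 | 0.877 | 2.093 | 3.6% |
| 5 | 12%, 41%, 78% | 0.1912 | 0.780 | 2.219 | 2.7% |

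**Step 2. Simulation, binary outcome** (30,000–40,000 trials per row; Monte Carlo error about 0.1 point on size). Regression means linear regression on arm and the two factors. CMH is the Cochran-Mantel-Haenszel test over the four strata. Power is at a log-odds effect of −1.5, about 43% v 14% when the factors have no effect.

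| OR per factor | Size: Chi-Square / CMH / regression | Power: Chi-Square / CMH / regression | Regression minus Chi-Square |
|---|---|---|---|
| 1 | 5.0 / 5.1 / 5.0% | 54.3 / 51.1 / 52.9% | −1.4 |
| 2 | 4.2 / 4.8 / 5.0% | 51.1 / 49.7 / 51.5% | +0.4 |
| 3 | 3.5 / 4.8 / 4.9% | 46.7 / 47.6 / 49.3% | +2.6 |
| 5 | 2.7 / 4.9 / 5.0% | 40.1 / 45.4 / 46.6% | +6.5 |

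The exact size of Chi-Square at 20 v 20 and 43% is 4.6%, so part of any gap can be discreteness. At a 20% event rate Chi-Square gives 4.7%, 4.2% and 3.7% at OR 2, 3 and 5. With minimisation probability 0.9 it gives 4.1%, 3.5% and 2.4%, and with 30% factor prevalence 4.2%, 3.8% and 3.0%. The regression 95% confidence interval for the risk difference covers 94.4–95.2%.

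**Step 3. Rank outcomes.** Each factor shifts the mean by 0, 0.38, 0.61 or 0.89 SD. Mann-Whitney size is 4.9%, 4.4%, 3.4% and 2.5%; regression of the ranks stays at 5.1–5.2%. Power at a 0.8 SD arm difference:

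| Factor shift (SD) | Mann-Whitney | van Elteren | Rank regression |
|---|---|---|---|
| 0 | 67.0% | 61.9% | 66.9% |
| 0.38 | 64.5% | 61.9% | 66.4% |
| 0.61 | 60.0% | 62.0% | 66.4% |
| 0.89 | 52.2% | 61.9% | 65.6% |

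**Step 4. Time outcomes** (43% events; factor hazard ratio 1, 2 or 3). Unstratified log-rank size is 5.1%, 4.2% and 3.0%; stratified 5.1–5.2%. Power at log hazard ratio −1.0, unstratified v stratified: 39.2 v 37.3%, 36.6 v 37.5%, 32.9 v 38.4%.

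**Step 5. Is balancing the cause?** Under unrestricted 1:1 randomisation with the same prognostic factors, the unadjusted tests stay at 4.6–5.8% for N = 40 (6,000 trials per row). The conservatism comes from balancing without adjusting.

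**Step 6. Site as a third minimisation factor** (three sites assumed, 60/25/15%). CMH over 12 strata has power 42.3%, 40.4% and 37.7% at OR 2, 3 and 5, against 50.8%, 48.6% and 45.2% for regression with site as a main effect. Between 25% and 38% of patients fall in strata that contribute nothing to that CMH test.

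**The case against.** **Low stakes.** This is a 40-patient feasibility study with no power target, the error is on the safe side, and power is poor whatever test is used: about 30% for 43% v 21.5% at 20 per arm. This stands and limits the weight of the point. Even so, the plan names a primary efficacy endpoint, ten comparative objectives and specific tests; tests that are run should match the design.

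**Small gain in ordinary cases.** At a smaller effect (log-odds −0.9, about 43% v 23%), Chi-Square v regression is 24.6 v 25.5% with both ORs 2, 21.0 v 23.5% with both 3, and 23.1 v 24.0% with only one factor prognostic at 3. Crossover, which Section 8 expects, would dilute the arm difference further. This also stands: the gain is 0–2.5 points unless the factors are strong, and OR 5 for both is a strong case.

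**Unconfirmed premise.** Section 4.4 mentions only sites. If pulse status and eGFR do not drive allocation, Chi-Square size is 4.4–5.0% and adjustment gains nothing at the same ORs. But Section 4.1 says patients are stratified on them and minimisation is the only allocation method described, so the natural reading is that they do. Section 4.4 needs an edit either way.

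**Unknown prognostic strength.** Section 4.1 speaks only of wound healing. The background lists kidney and arterial disease for revision, without effect sizes and without pulse status, and Section 4.2 excludes severe arterial disease not being revascularised. The condition must therefore stay in the conclusion.

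**Conclusion.** The point holds, conditionally and at modest size. If pulse status and eGFR group are prognostic and enter the minimisation, the planned tests are conservative: Chi-Square runs at about 4.2%, 3.5% and 2.7% at ORs of 2, 3 and 5 per factor, and main-effects regression recovers about 0, 2–3 and 6 points of power. For rank outcomes the recovery is larger: about 2, 6 and 13 points at the corresponding shifts. These figures rest on the assumed prevalence, event rate and minimisation probability. The direction holds at a 20% event rate, at 30% prevalence and at minimisation probability 0.9.

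False positives are not inflated and the feasibility objective is unaffected. The change is worth making because it is cheap and aligns the analysis with the allocation. The missing factor list, the eGFR boundary and the absent time-to-event test need correcting whatever the prognostic strength.

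**What to change.** **Sections 4.1 and 4.4.** List the minimisation factors: pulse status, eGFR group and, if used, site. Write the eGFR levels as ≥60 and <60 wherever they appear.

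**Section 8.** Add, in substance:

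> Between-arm comparisons will include pulse status and eGFR group (and site, if used in minimisation) as main effects. Binary outcomes: risk difference with 95% CI from a linear regression on arm and these terms. Skewed or ordinal outcomes: regression of the ranks on the same terms. Time outcomes: log-rank test stratified by pulse status and eGFR group, alongside the Kaplan-Meier curves. Unadjusted tests are sensitivity analyses. Event counts will be shown by arm; where events are few, counts alone will be reported.

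With the two factors only, a Mantel-Haenszel risk difference with CMH test, or van Elteren for ranks, is acceptable. Site should not be crossed into the strata. If the team prefers to label all between-arm comparisons descriptive and drop the tests, that also resolves the mismatch, but Section 4.4 still needs its list.

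**Cost.** Wording only; both factors are already needed for stratification. The edit should precede any unblinded comparison. If the factors are not prognostic, adjusting costs about 1.5 power points for the binary regression (3 for CMH), none for rank regression (5 for van Elteren) and 2 for the stratified log-rank. For rare outcomes such as the events in Section 7.1, adjustment adds little.

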3.2.2 Primary Safety Endpoint

The primary safety endpoint is the rate of vascular-related post-operative complications in each group.

4. Study Participants:

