9.2 Data Protection

All data shall be managed in the strictest confidence by approved trial investigators in accordance with Irish data-protection law. Datasets will be anonymous, encrypted and stored in a secure centralised sever (REDCap).

10. Discussion:

At present, ray amputation can be performed using a bone cutters or a bone saw to transect the metatarsal shaft, depending on institutional availability and surgeon preference. There is a dearth of published literature comparing outcomes achieved between the two techniques.

Certainly, there has been no randomised controlled trials published. This randomised controlled feasibility study aims to provisionally compare the value and safety profile of two different surgical techniques. An initial feasibility study was selected as a significant number of patients are needed to power a full study. We plan to recruit from multiple sites after the initial cohort has been selected.

References:

2. Emerging Risk Factors C, Sarwar N, Gao P, Seshasai SR, Gobin R, Kaptoge S, et al. Diabetes mellitus, fasting blood glucose concentration, and risk of vascular disease: a collaborative meta-analysis of 102 prospective studies. *Lancet*. 2010;375(9733):2215-22.

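### Binary outcomes, including the primary safety endpoint, are to be analysed by a Chi-Square test with no between-arm estimate or confidence interval, and at 20 per arm the p-value says little about remaining harm

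*Combined protocol and SAP*

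**What the plan says.** Section 3.2.2 sets the safety outcome: "The primary safety endpoint is the rate of vascular-related post-operative complications in each group". Section 10 (Discussion) says that the study "aims to provisionally compare the value and safety profile of two different surgical techniques". Section 2.1 makes the primary objective the collection of data good enough for the power calculation of a future trial.

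Section 8 (Statistical considerations) gives the size, "we aim to recruit 20 patients into each arm i.e. 40 patients in total", and explains the lack of a formal justification: "as such there is no data on which to base a power calculation". On method it says "Binary outcomes will be analysed using the Chi-Square test". That sentence is generic and does not name the safety endpoint, but whether a patient had a complication is a binary outcome and no other binary method is given. Section 8 names no significance level, effect measure, confidence interval, margin or upper bound, and no other section does so. Section 7.1 adds that the listed adverse events will be recorded and reported.

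**The concern.** A Chi-Square test returns a p-value. It does not say how large the difference between the saw and the cutter is, or how large a difference the data leave open. In a trial of 40 patients the second question matters most for safety, because a non-significant result is likely whether or not one tool is materially worse. Those deciding on a full trial could take comfort from such a result that the data do not support.

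The plan also fits its own primary objective poorly. A later sample-size calculation needs event rates and a view of their uncertainty, and a p-value supplies neither.

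**Working it through.** **Inputs from the documents.** 20 per arm, 40 in total, 1:1 (sections 4.4 and 8); Chi-Square test for binary outcomes (section 8). The sample size has no power calculation behind it, so the only check on it is 20 + 20 = 40, which agrees.

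**Assumptions.** Two-sided 5% level; no continuity correction; all 40 patients followed; a doubled rate as the harm of interest. The documents give no rate for vascular-related complications, so lower-arm rates from 5% to 30% are used. The nearest figure is in the background section, where, of 146 patients with minor amputation, 63 needed further ipsilateral amputation, "21 (14.4%) of which were trans-tibial or trans-femoral" (21/146 = 14.4%). Section 7.1 lists the same kind of event: "Major ipsilateral amputation, either below-knee amputation or above-knee amputation". It is one possible component in a different cohort, so it serves only as an anchor.

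**Step 1: chance that a doubling is non-significant.** With a events in one arm and b in the other, n = 20 per arm:

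X² = 2n[a(n − b) − b(n − a)]² / [(a + b)(2n − a − b)n²], significant if X² > 3.841.

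The probability of non-significance is the sum of Bin(a; 20, p) × Bin(b; 20, 2p) over all 21 × 21 tables with X² ≤ 3.841.

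| Rates | Uncorrected Chi-Square | Continuity-corrected | Fisher exact |
|---|---|---|---|
| 5% vs 10% | 94.6% | 99.5% | 98.3% |
| 10% vs 20% | 86.2% | 94.9% | 92.8% |
| 14.4% vs 28.8% | 80.4% | 89.2% | 88.2% |
| 15% vs 30% | 79.5% | 88.5% | 87.6% |
| 20% vs 40% | 70.9% | 82.4% | 80.8% |
| 25% vs 50% | 62.5% | 76.1% | 73.1% |
| 30% vs 60% | 53.7% | 67.6% | 65.3% |

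For the uncorrected test the figure falls below 80% once the lower rate exceeds about 14.7%.

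**Step 2: what an interval adds.** The Wilson 95% limits for x/n are [p + z²/(2n) ± z√(p(1 − p)/n + z²/(4n²))] / (1 + z²/n), with p = x/n and z = 1.96. For 3/20:

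- centre = (0.15 + 0.0960)/1.1921 = 0.206
- half-width = 1.96 × √(0.006375 + 0.002401)/1.1921 = 0.154
- limits = 0.052 to 0.360

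The Newcombe interval combines the two arms' Wilson limits. For 3/20 vs 3/20 it is 0 ± √[(0.15 − 0.052)² + (0.360 − 0.15)²] = ±0.232. So p = 1 goes with an interval of -23 to +23 percentage points.

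For 7/20 vs 2/20, X² = 40 × (7 × 18 − 2 × 13)² / (9 × 31 × 400) = 400,000/111,600 = 3.58, p = 0.058. This is non-significant, yet the difference is +25 points with a Newcombe interval of -1 to +48.

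**Step 3: is the Chi-Square test itself unsound here?** By the same enumeration with equal rates in both arms, the type I error of the uncorrected test is 1.2% at 5%, 3.9% at 10%, 4.9% at 14.4%, 5.0% at 20%, 5.3% at 30% and 4.8% at 40%. It is conservative or close to nominal throughout.

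**The case against.** The strongest reply is that low power is expected and openly acknowledged. The plan calls itself a feasibility study, says that no power calculation was possible, and describes the safety comparison as provisional. That stands: the miss rates in step 1 are not in themselves a fault, and adding intervals will not change them.

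It is also fair that section 3.2.2 already defines the endpoint as a rate in each group, so per-arm rates will presumably be shown and a reader could derive an interval from counts out of 20. This reduces the harm. It does not make the interval a planned result or settle how the comparison will be interpreted.

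A reader might infer three stronger points, none of which the documents or the arithmetic support:

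- **That a doubled rate would be missed at least 80% of the time whatever the baseline.** This fails above a lower-arm rate of about 15% with the uncorrected test, and the documents give no rate for the endpoint. If it covers the events listed in section 7.1, its rate could be higher than that of major amputation alone.
- **That the plan equates non-significance with equal safety.** No section says so, and no equivalence claim, safety decision rule or progression rule rests on the p-value. The misreading is a risk, not a stated intention.
- **That small expected counts make Chi-Square a poor fit and call for an exact test.** Step 3 shows no material inflation of type I error, and Fisher's test would raise the miss rate from 80% to 88% at 14.4% vs 28.8%.

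**Conclusion.** The concern holds as a gap in reporting and analysis. The one method planned for binary outcomes yields no between-arm estimate and no interval, although the study has a primary safety endpoint, intends a provisional safety comparison and must inform a future power calculation.

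Its size depends on an unknown rate. Under the assumptions listed in the working, the uncorrected test would leave a doubling non-significant about 80% to 95% of the time for lower-arm rates from about 15% down to 5%, about 71% at 20% vs 40%, and less often at higher rates. The interval result does not rest on an assumed true rate: if 3 of 20 patients in each arm have an event, differences of up to 23 points in either direction remain compatible with the data. The change is worth making because it costs almost nothing, but it does not call the design or the sample size into question.

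**What to change.** In section 8, for the primary safety endpoint and preferably for all binary outcomes, replace the Chi-Square sentence with wording such as:

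*For each arm, the number and percentage of patients with an event will be reported with a Wilson 95% confidence interval. The difference between arms (saw minus cutter) will be reported with a Newcombe or Miettinen-Nurminen 95% confidence interval as the main result. The Chi-Square p-value will be secondary. A non-significant result will not be read as evidence that the two tools are equally safe; the confidence limits show the excess risk that has not been excluded.*

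Name one of the two interval methods in advance. The change needs no extra patients, visits or data. Its cost is presentational: the intervals will be wide, and the comparison will look less conclusive than a single p-value.
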